9.1. Description of some research procedures

9.1.1. Anamnesis

Collection of the anamnesis of the studied disease will be carried out during the screening, as well as information on significant past or current concomitant diseases

(for example, allergic reactions, congenital and acquired heart and vascular diseases, other serious diseases, organ transplantation, mental disorders).

9.1.2. Collection of information about concomitant and previous therapy

All medications taken within 30 days prior to screening must be registered in the primary documentation. Separately, it will be clarified whether the patient took any prohibited drugs that prevent his/her inclusion in the trial.

9.1.3. Physical examination

Physical examination should be performed by the investigator. It includes (at a minimum) assessment of the patient's general condition and the following body systems: lymph nodes, mouth, and pharynx, lungs, cardiovascular system, abdominal cavity, extremities, musculoskeletal system, nervous system, and skin.

All changes considered clinically significant should be reported as an anamnesis before the study drug administration, and after the patient received the study drug, all changes should be reported as adverse events.

9.1.4. Vital signs

Vital signs include blood pressure, heart rate, and respiratory rate, which must be measured and recorded by the staff of the research center.

Measurements of blood pressure and heart rate should be taken at the same body position throughout the trial.

9.1.5. Electrocardiography

Electrocardiography (ECG) is performed in accordance with normal clinical practice. A prerequisite is the registration of all 12 standard leads.

ECG interpretation is performed by an authorized researcher. It is necessary to indicate the date of ECG registration and provide a general conclusion. ECG records should be kept in the CRF.

9.1.6. CTPA

The most common method for PE diagnosing is computed tomography of the pulmonary arteries (CTPA, level of evidence 1A). It has broad capabilities for

visualizing the lumen of the pulmonary arteries, the nature of damage to the vascular bed, identifying pulmonary infarctions, and, while simultaneously performing a native study of the lungs, to make a differential diagnosis.

The presence of PE is undoubted when thrombi are detected in the segmental (distal) and more proximal branches of the pulmonary arteries.

Currently, CTPA is the standard for PE non-invasive diagnosis due to its high sensitivity and specificity.

The embolic lesion system is assessed using the Qanadli index [15]. The Qanadli index in the absence of lesion is 0, in case of partial lesion – 1 and in case of complete lesion – 2.

In the Qanadli system, each lung is divided into 10 segments (20 in total), i.e. The maximum Qanadli index with complete damage to both lungs will be 40. Qanadli index was calculated by dividing the patient score by the maximal total score (40) and by multiplying the result by 100 at baseline and 24 h after drug administration.

Interpretation of the CTPA results will be performed by certified specialists who are unaware of the goals and objectives of this clinical trial and the therapy performed.

9.1.7. EchoCG

EchoCG is an informative and accessible non-invasive method for examining patients with PE. According to EchoCG, PE presence can be predicted or denied with high accuracy. EchoCG examination has many fairly specific symptoms for PE diagnostics. PE is supported by: enlargement of the right chambers of the heart, bulging of the interventricular septum towards the left parts, paradoxical movement of the interventricular septum in diastole, direct location of the thrombus in the pulmonary artery, severe regurgitation on the tricuspid valve, 60/60 sign, McConnell sign.

Positive echocardiography results may be the basis for PE diagnosis.

The criterion for right ventricular dysfunction (RVD) is an increase in pulmonary artery systolic pressure (PASP) of more than 30 mm Hg in combination with RV enlargement more than 30 mm. The following parameters are also assessed: right atrium diameter, RV/LV end-diastolic (EDD) ratio, RV free wall hypokinesis, thrombosis of the right chambers heart, paradoxical movement and/or flattening of the interventricular septum.

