8. DESIGN AND PLAN OF RESEARCH ACTIVITIES

This trial is a multicenter, open-label, randomized, parallel-group, phase III b non-inferiority trial to compare the efficacy and safety of the trial drug.

The trial will include 310 patients with massive PE. The patients will be monitored for 30 days: 1-2 days in the Intensive Care Unit and the Department of cardiology in the remaining days before discharge (on average 14 days), with an outpatient visit on the 30th day.

Start of research, initiation of centers: «_____» 20____

Enrollment of patients: «_____» 20____

Result processing and reporting: «_____» 20____

The enrollment period may be extended to total patient enrollment if a research center fails to enroll the planned number of patients. The end date of the trial is considered to be the end date of the trial in all patients involved.

In each research center, the subject of the trial is assigned a serial number that corresponds to the sequence of patient inclusion in the trial. The serial number is reflected in the CRF. The list of patient's identification is stored in the trial file. Patients are included in the trial only after signing the Informed consent form.

Before the trial, all patients will undergo the following procedures: collection of thorough medical history, signs of hemodynamic collapse, risk stratification to assess the prognosis according to the PESI classification, a physical examination, CTPA, ECG, EchoCG with the definition of PASP, ultrasound diagnostics of the inferior vena cava will be performed; blood and urine samples will be taken for laboratory tests:

- **complete blood count:** hemoglobin, red blood cells, hematocrit, leukocyte formula: neutrophils, eosinophils, basophils, monocytes, lymphocytes, platelets, ESR;
- **biochemical blood parameters:** total protein, creatinine, urea, AST, ALT, CK, NT-proBNP, total bilirubin, glucose, sodium, potassium, total cholesterol, HDL-cholesterol, triglycerides;

- **coagulogram:** fibrinogen, aPTT, INR, prothrombin, D-dimer.
- **general urine analysis:** red blood cells.

After enrollment, patients will be randomized using the «envelope method» into two equal groups of 155 patients each (a total of 310 people, including 10% who may have dropped out) and assigned to receive either Fortelyzin® or Actilyse®. Fortelyzin® will be given as single i.v. bolus over 10-15 seconds. Actilyse® will be administered following the instruction for use.

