To compare the efficacy and safety of Fortelyzin® vs Actilyse®, patients will be monitored for 3 days after administration of the drug. During this period, patients will have 6 visits (Table 5).

Table 5. FORPE trial plan

Procedure	Visit number and its period	V ₁	V ₂	V ₃	V ₄	V ₅	V ₆
		0	Day 1	Day 2	Day 7	At discharge	Day 30 (outpatient)
Inclusion and exclusion criteria		+	–	–	–	–	–
Signing informed consent form		+	–	–	–	–	–
Demographics		+	–	–	–	–	–
Anamnesis		+	–	–	–	–	–
Previous treatment		+	–	–	–	–	–
PESI risk stratification		+	–	–	–	–	–
CTPA		+	+	–	–	–	–
EchoCG with PASP definition		+	+	–	+	+	–
Ultrasound diagnostics of the inferior vena cava		+	+	–	+	–	–
Assessment of vital signs		+	+	+	+	+	+
Determining the presence of hemodynamic collapse		+	+	+	+	–	–
Physical examination		+	–	–	–	–	–
Accompanying illnesses		+	–	–	–	–	+
Changes in organs and systems		–	+	+	+	+	–
ECG		+	+	–	+	+	–
Coagulogram		+	+	–	–	–	–
General blood test		+	+	–	+	+	–
Biochemical blood test		+	–	–	–	+	–
General urine test		+	+	–	–	+	–
Fortelyzin® or Actilyse® administration		+	–	–	–	–	–
Concomitant therapy changes		–	+	+	+	+	+
Registration of AE and SAE		–	+	+	+	+	+
Assessment of bleedings		–	+	+	+	+	–

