11. EFFICACY ENDPOINTS

- Primary efficacy outcome – death from any causes within 7 days;
- Secondary efficacy outcome – PASP (V1, V2, V4, V5);
- Secondary efficacy outcome – hemodynamic collapse within 7 days;
- Secondary efficacy outcome – recurrent PE within 7 days;
- Secondary efficacy outcome – death from PE within 7 days;
- Secondary efficacy outcome – death from any causes within 30 days;
- Secondary efficacy outcome – clinical composite of hemodynamic collapse within 7 days + recurrent PE within 7 days + death from any causes within 30 days.

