13. CASE REPORT FORM

Primary data means all the information contained in the original medical records and their certified copies, describing the results of clinical observations, examinations, and other activities, allowing to restage the trial and assess it. Primary data is included in the primary documentation (originals or certified copies thereof).

Data entered in the CRF will be confirmed by other primary documents.

For the tests performed in the central laboratory, it is necessary to attach a copy of the analysis results to the CRF.

It is necessary to attach CTPA data on CD media, ECG, EchoCG with description, and an ultrasound protocol of the inferior vena cava system to the CRF.

Erroneous records are crossed out with a single line so that it can be read. Correct records are made nearby. All records and corrections are dated and signed by the physician-investigator.

The original documents should be available for periodic review. The original CRFs are transferred to the Sponsor upon completion of the trial.

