18. STATISTICAL ANALYSIS OF TRIAL RESULTS

All indicators entered into the clinical database will be listed for each patient and sorted by group (Fortelyzin® or Actilyse®), patient number and visit.

Statistical analysis was carried out using R Foundation for Statistical Computing и Graph Pad Prism 7, Graph Pad Software Inc (version 4.2). Continuous variables will be presented as mean (SD) or median (IQR). Categorical variables will be presented as n (%) and corresponding 95% Clopper-Pearson confidence intervals (CI).

Mann-Whitney U test will be used to compare continuous variables and the two-sided Fisher's exact test will be used to compare categorical variables.

Odds ratios (ORs) will be estimated and presented with 95% CIs. Outcomes will be considered as statistically significant if the p value will less than 0,05.

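### The plan masks CTPA readers to treatment but sets no such rule for the echocardiography that yields PASP, the only continuous efficacy outcome in this open-label trial

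*Combined protocol and SAP*

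**What the plan says.** On treatment masking, section 8 (Design and plan of research activities) is plain: "This trial is a multicenter, open-label, randomized, parallel-group, phase III b non-inferiority trial". One arm receives a bolus over 10 to 15 seconds, the other a bolus plus infusion.

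For CTPA, section 9.1.6 assigns interpretation to "certified specialists who are unaware of the goals and objectives of this clinical trial and the therapy performed". That section also defines the Qanadli index at baseline and 24 hours. The index does not appear among the efficacy endpoints in section 11.

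For echocardiography, section 9.1.7 starts "EchoCG is an informative and accessible non-invasive method for examining patients with PE" and then describes the signs of PE, the criterion for right ventricular dysfunction and the other parameters assessed. It names no operator or reader, sets no masking and provides for no central reading.

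The visit table in section 8 has the row "EchoCG with PASP definition", marked at V1, V2, V4 and V5. Section 11 lists PASP at those four visits as a secondary efficacy outcome. The other six efficacy outcomes are binary: all-cause death at 7 and 30 days, death from PE, hemodynamic collapse, recurrent PE and a composite.

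Section 13 (Case report form) says what is kept: "It is necessary to attach CTPA data on CD media, ECG, EchoCG with description". Storage on disc is specified for CTPA only.

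Section 18 gives the analysis: "Mann-Whitney U test will be used to compare continuous variables", and "Outcomes will be considered as statistically significant if the p value will less than 0,05".

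**The concern.** PASP is a number that an operator obtains and measures, so knowledge of the arm can move it. In section 9.1.6 the plan already treats this as a risk worth guarding against for imaging. The same guard is missing where imaging produces a listed efficacy outcome.

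At stake is the reading of any PASP difference. A systematic measurement shift between arms would pass straight into the Mann-Whitney comparison and be reported as a drug effect, or it could hide one. Analysis cannot remove a shift introduced at measurement. A masked re-reading later might not be possible either, because section 13 asks for the echocardiogram with its description and does not clearly require stored images.

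V1 is not exposed in the same way: section 9 lists the echocardiogram before randomization at that visit. The exposed visits are V2, V4 and V5.

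**Working it through.** **Sample size used.** Section 17 assumes 10% mortality in each arm, a 10-point margin, one-sided 2.5% and 80% power. Its formula gives n = (1.960 + 0.842)² × (0.09 + 0.09) / 0.10² = 141.28 per arm. The plan states 141, so its figure is reproduced apart from rounding (142 if rounded up). Multiplying 141 by 1.1 gives 155.1, the stated 155 per arm. I use 141 as the number measured.

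**Assumed inputs.** The documents give neither an SD for PASP nor any estimate of reader bias. I assume a between-patient SD of 10, 15 or 20 mm Hg and a net between-arm shift b of 2, 3 or 5 mm Hg, with no true treatment difference. I take p<0.05 as two-sided. Each figure is for one visit.

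**Smallest difference that reaches significance.** SE = SD × √(2/141) = 0.1191 × SD. The threshold is 1.96 × SE = 0.233 × SD, which is 2.3, 3.5 and 4.7 mm Hg for SD 10, 15 and 20. If the expected 10% deaths leave about 141 × 0.9 = 127 per arm, it is 2.5 to 4.9 mm Hg. With all 155 it is 2.2 to 4.5 mm Hg.

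**Chance of p<0.05 from a shift alone.** In the normal approximation this is Φ(b/SE − 1.96) + Φ(−b/SE − 1.96). For SD 15 and b = 3, SE = 1.79 and b/SE = 1.68, which gives 0.39. The planned Mann-Whitney test, in 4,000 simulated trials per setting with normal data, gives slightly lower or similar values:

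| Assumed SD (mm Hg) | No shift | 2 mm Hg | 3 mm Hg | 5 mm Hg |
|---|---|---|---|---|
| 10 | 5% | 36% | 69% | 98% |
| 15 | 5% | 19% | 37% | 78% |
| 20 | 5% | 13% | 24% | 52% |

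The normal approximation for 3 mm Hg is 71%, 39% and 24%, so the two methods agree closely. A shift of only 1 mm Hg gives 13%, 9% and 7% by that approximation, little above the nominal rate.

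**General rule.** A shift of (1.960 + 0.842) × 0.1191 = 0.334 SD gives an 80% chance of p<0.05. That is 3.3, 5.0 and 6.7 mm Hg for the three SDs.

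**The case against.** The strongest reply is that these figures show sensitivity, not bias. At this sample size a fixed shift of a third of an SD will usually be significant for any continuous outcome. In a multicenter trial the shift would also have to be a net one, in the same direction across many operators. This stands: the shifts are assumptions, and their size, direction and likelihood are unknown.

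A reader might infer that the treating investigator, knowing the arm, measures PASP. The documents do not say so. Section 9.1.3 names the investigator for the physical examination and section 9.1.5 an authorized researcher for the ECG, but section 9.1.7 names nobody. What is established is the absence of a requirement.

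A reader might also infer that the masking was spent on a test that serves no efficacy outcome. That goes too far. Recurrent PE within 7 days is a listed outcome and part of the composite, the plan does not say how it is confirmed, and section 9.1.6 treats CTPA as the standard non-invasive diagnostic test. Masked CTPA reading may support it. The documents show only that the Qanadli index is not a listed endpoint.

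Finally, PASP is secondary. The non-inferiority margin and sample size in section 17 rest on mortality, and nothing makes a PASP p-value decisive. This also stands, and it limits the weight of the point. It does not remove the gap, because PASP is a listed outcome and section 18 applies a significance rule to it.

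**Conclusion.** The point holds in limited form. The plan requires masked interpretation of CTPA, has no matching rule for the echocardiography that gives PASP, and supplies none elsewhere. Unmasked measurement of the only continuous efficacy outcome is therefore allowed.

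If a net 3 mm Hg shift occurred with no true difference, p<0.05 would follow in about 24% to 69% of trials per visit. For 2 mm Hg the range is about 13% to 36%, against about 5% with no shift. These figures rest on the assumed SD range, the assumed shifts, normally distributed data and 141 measured patients per arm.

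They do not support the stronger reading that PASP will be biased or that the trial's main conclusion is at risk. All-cause death within 7 days does not depend on echocardiographic reading.

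**What to change.** Add to section 9.1.7 that PASP at V2, V4 and V5 is measured by the site's existing echo staff who, wherever possible, are not treating the patient and are not told the assigned drug, and that the request form omits it. Add two CRF items: the operator, and a yes/no field for whether the operator was aware of the allocation. In section 18, plan a sensitivity analysis of PASP restricted to measurements by unaware operators. Awareness is recorded after randomization and may differ between arms, so that analysis should support the full comparison and not replace it.

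The cost is a short addition to 9.1.7, two CRF items and some rostering effort. No extra reader, scan or visit is needed, and sample size and treatment are unchanged. Masking may be incomplete at V2, when patients are in intensive care and the operator may see the chart or speak to staff. The awareness field is there to show how often that happens.

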9.1.8. Ultrasound diagnostics of the inferior vena cava

The study is carried out to identify PE source (thrombosis) and the likelihood of recurrent PE (the presence of floating blood clots). The deep veins of the leg, popliteal veins, superficial femoral veins, common and deep femoral veins, external and common iliac veins, the inferior vena cava, as well as the great and small saphenous veins are examined on both limbs. If there is no thrombosis in these veins, it is necessary to examine the internal iliac, gonadal (testicular), renal and hepatic veins. A reliable sign of thrombosis should be considered the absence of closure of the vein walls during compression by a sensor installed across the vein.

9.1.9. General and biochemical blood analysis

The tests are carried out in accordance with the methodology adopted in the clinical site laboratory. The following parameters will be measured:

- general blood count (number of red blood cells, white blood cells, platelets, hemoglobin, hematocrit, leukocyte formula, ESR)
- biochemical blood parameters (glucose, NT-proBNP, ALT, AST, bilirubin, creatinine, total protein, sodium, potassium, CK, urea, cholesterol, HDL-C, triglycerides)
- coagulogram (fibrinogen, INR, APTT, prothrombin, D-dimer)

In the case of clinically significant abnormalities, these phenomena are recorded as a concomitant disease (during the screening) or as an adverse event (during the trial).

9.1.10. General urine analysis

To perform the analysis, approximately 50 ml of the first-morning portion of urine is taken, and the analysis is carried out according to local practice. The quantity of red blood cells will be measured.

In the case of clinically significant abnormalities, these phenomena are recorded as a concomitant disease (during the screening) or as an adverse event (during the trial).

10. THERAPY DURING THE TRIAL

Study drug: Fortelyzin®

Manufacturer: «SuperGene», LLC, Russia

Drug description

Pharmaceutical form: lyophilizate for preparation of a solution for intravenous administration, supplied with a solvent

Detailed description:

Lyophilizate: tablet-like freeze-dried mass of white or almost white color.

Solvent: colorless transparent liquid.

Reconstituted solution: colorless, transparent or slightly opalescent liquid.

Composition:

Active substance: Forteplase® (recombinant protein containing the amino acid sequence of staphylokinase) 5 mg (745 000 IU).

Excipients: L-arginine – 15,0 mg, L-histidine – 2,0 mg, glycine – 30,0 mg, povidone-17 – 20,0 mg, polysorbate-20 – 0,4 mg.

Solvent: 5mL ampule of sodium chloride 0.9% solution for injection

Dosage regimen: Fortelyzin® will be assigned at a dose of 15 mg (2 235 000 IU).

Route of administration: intravenously in the form of a single bolus injection for 10-15 sec. The solution of Fortelyzin® is prepared immediately before administration: the content of a 5 mg vial (745 000 IU) is diluted in 5 ml of 0.9% sodium chloride solution. Non-storable!

Labeling: «Product for clinical trial only».

Active Comparator: Actilyse®**Manufacturer:** Boehringer Ingelheim Pharma GmbH & Co. KG**Drug description****Pharmaceutical form:** lyophilizate for preparation of a solution for infusion supplied with a solvent.**Detailed description:**

Lyophilizate: freeze-dried mass of white or light yellow color.

Solvent: colorless transparent liquid

Composition:

Active substance: Alteplase 50,0 mg

Excipients: L-arginine: 1742 mg,

Phosphoric acid, 85 %: up to pH 7,2 ± 0,2,

Polysorbate 80: 3,5-5,0 mg.

The excess is 3,5 % of the nominal amount of the active ingredient and excipients in the vial.

Residual traces: gentamicin (used in the production process).

Each vial of solvent contains:

Water for injection: 50 ml

1 ml of the solution after dilution contains 1 mg of alteplase.

Dosage regimen:

Actilyse® is administered in accordance with the instructions for use in ischemic stroke at a dose 100 mg.

Labeling: «Product for clinical trial only».

Previous treatment

Every effort should be made to find out what treatment the patient received within 30 days before administration of the study drug. The names of the drugs, the start and end dates of their use should be registered in the CRF.

Permitted concomitant therapy

In the first 24 hours after thrombolysis, the use of drugs to lower blood pressure is allowed: angiotensin-converting enzyme inhibitors and angiotensin receptor antagonists. If blood pressure drops during thrombolysis, the use of vasopressors (dobutamine, dopamine, and norepinephrine) is allowed.

Patients treatment is carried out in accordance with current Guidelines [1, 2].

After thrombolysis, anticoagulant therapy with unfractionated heparin must be started within 48 hours:

– intravenously with a bolus of 80 units/kg (or 5000 units) and infusion at an initial rate of 18 units/kg/h (or 1250-1300 units/h), then dose selection according to aPTT values. The goal is to maintain an aPTT of 1,5 to 2,5 times the laboratory-specific upper limit of normal (or anti-Xa activity values of 0,6 to 1,0 units/mL using the amidolytic method).

If anticoagulant therapy with unfractionated heparin is initiated at the prehospital stage, an intravenous bolus is not administered, but its infusion is continued.

After 48 hours, a switch is made to low molecular weight heparin, which is administered for 7 days:

– Enoxaparin sodium – subcutaneously 100 units (1 mg/kg) 2 times a day followed by indirect anticoagulants:

– Vitamin K antagonists – orally, dose selection in order to maintain the INR in the range from 2 to 3;

or NOACs:

– Dabigatran etexilate – 150 mg orally 2 times daily;

– Rivaroxaban – 15 mg orally 2 times a day for 21 days, then 20 mg once daily;

– Apixaban – 5 mg orally 2 times daily.

Anticoagulants are taken for at least 6 months.

In case of an allergic reaction during thrombolysis, the use of glucocorticoids and antihistamines is permitted.

In case of severe bleeding (especially from non-compressible vessels), the administration of thrombolytics should be discontinued. The administration of fresh frozen plasma or fresh blood is indicated.

Prohibited concomitant therapy

In patients with massive PE, massive fluid resuscitation is not recommended because aggressive volume loading may worsen right ventricular dysfunction.

